#### **8.15.3. Sponsor Reporting Requirements to Regulatory Authorities**

AE reporting, including suspected unexpected serious adverse reactions, will be carried out in accordance with applicable local regulations.

### **9. DATA ANALYSIS/STATISTICAL METHODS**

Detailed methodology for summary and statistical analyses of the data collected in this study will be documented in a Statistical Analysis Plan (SAP), which will be maintained by the Sponsor. This document may modify the plans outlined in the protocol; however, any major modifications of the primary endpoint definition and/or its analysis will also be reflected in a protocol amendment.

#### **9.1. Sample Size Determination**

The primary objective of the study is to demonstrate the non-inferiority in efficacy of tofacitinib 11 mg MR QD to 5 mg IR BID for the treatment of signs and symptoms in patients with active RA on a stable background of MTX, as measured by DAS28-4(CRP) change from baseline at Week 12.

The following assumptions in treatment comparison for the primary endpoint have been applied: (1) one-sided type-I error (alpha) of 0.025, (2) subjects assigned to tofacitinib MR 11 mg QD and IR 5 mg BID groups in a 1:1 ratio, (3) difference of treatment means is zero, (4) a common standard deviation of 1.3 based on the previous tofacitinib studies. Based on the forgoing assumptions, a total of at least 200 evaluable subjects (100 in each treatment arm) will be required to demonstrate non-inferiority with a power of 90% and a non-inferiority margin of 0.6, which is equal to the minimum improvement in disease activity by DAS consistent with a “moderate response” by the European League Against Rheumatism (EULAR) criteria.

It is anticipated that the sample size of 100 subjects in each formulation group will provide 0.36 half-width of 2-sided 95% confidence interval for the difference on the change from baseline in DAS28-4(CRP) at Week 12 assuming a common standard deviation of 1.3.

## **9.2. Efficacy Analysis**

### **9.2.1. Statistical Hypothesis**

The primary hypothesis associated with the statistical objective is to demonstrate non-inferiority of tofacitinib MR 11 mg QD to IR 5 mg BID as measured by DAS28-4(CRP) change from baseline at Week 12. The null hypothesis is that the treatment difference (tofacitinib MR 11 mg QD – IR 5 mg BID) is 0.6 or more, and the alternative hypothesis is that the treatment difference is less than 0.6.

### **9.2.2. Statistical Decision Rule**

If the lower bound of the 2-sided 95% confidence interval (type-I error [alpha] of 0.025 in each tail) for the difference in change from baseline in DAS28-4(CRP) between the two arms (MR 11 mg QD – IR 5 mg BID) is less than 0.6, then the treatment of tofacitinib MR 11 mg QD will be declared to be non-inferior to that of tofacitinib IR 5 mg BID.

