### **STATISTICAL METHOD**

The primary efficacy endpoint, DAS28-4(CRP), will be expressed as a change from Baseline. The analysis will be conducted using a linear mixed effect model with repeated measures (MMRM), which will include baseline as a covariate, treatment, visit (week 4 and 12), and treatment by visit interaction as fixed effects. Subjects will be a random effect and unstructured covariance will be assumed. The estimate of treatment difference and the associated 2-sided 95% confidence interval (type-I error [ $\alpha$ ] of 0.025 in each tail) at the primary time point of week 12 will be made from this model. Non-inferiority of tofacitinib MR 11 mg QD to IR 5 mg BID will be concluded if the lower bound of the 2-sided 95% confidence interval is greater than the pre-specified non-inferiority margin of  $-0.6$ .

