### **4.2. Statistical Decision Rules**

*If the upper bound of the 2-sided 95% confidence interval (type-I error [alpha] of 0.025 in each tail) for the difference in change from baseline in DAS28-4(CRP) between the two arms (MR 11 mg QD – IR 5 mg BID) is less than 0.6, then the treatment of tofacitinib MR 11 mg QD will be declared to be non-inferior to that of tofacitinib IR 5 mg BID.*

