## **8.2. Statistical Analyses**

### **8.2.1. Analysis of Primary Efficacy Endpoints**

The primary endpoint DAS28-4(CRP) change from baseline will be analyzed using MMRM described in Section 8.1.1 on the FAS. The patient is required to have a baseline and at least one non-missing on-study assessment of DAS28-4(CRP) to be included in the analysis. Missing values will not be imputed.

Non-inferiority of tofacitinib MR 11 mg QD to IR 5 mg BID will be concluded if the upper bound of the 2-sided 95% confidence interval of differences between the treatment groups (MR 11 mg QD – IR 5 mg BID) at Week 12 is less than the pre-specified non-inferiority margin of 0.6.

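### Protocol 9.2.2 compares the wrong confidence bound with the 0.6 margin: read literally, it declares non-inferiority 97.5% of the time when MR is worse by the full margin; the SAP has the correct rule

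*Protocol*

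**What the plan says.** Protocol 9.2.1 defines the treatment difference as MR 11 mg QD minus IR 5 mg BID. The null is a difference of 0.6 or more, "and the alternative hypothesis is that the treatment difference is less than 0.6".

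The current documents word the decision rule in three ways:

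- **Protocol 9.2.2** begins "If the lower bound of the 2-sided 95% confidence interval (type-I error [alpha] of 0.025 in each tail" and, for MR minus IR, requires that bound to be below 0.6. Section 9.2.3 refers the reader to 9.2.2 for the rule.
- **Protocol Summary, Statistical Method**: non-inferiority "will be concluded if the lower bound of the 2-sided 95% confidence interval is greater than the pre-specified non-inferiority margin of" −0.6. The direction of subtraction is not given.
- **SAP 4.2** begins "If the upper bound of the 2-sided 95% confidence interval" and requires it to be below 0.6 for MR minus IR. **SAP 8.2.1** repeats this: non-inferiority is "concluded if the upper bound of the 2-sided 95% confidence interval of differences between the treatment groups" is below 0.6.

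The design in Protocol 9.1 assumes a "one-sided type-I error (alpha) of 0.025", and states that 200 evaluable subjects "will be required to demonstrate non-inferiority with a power of 90% and a non-inferiority margin of 0.6". Protocol section 9 lets the SAP modify the protocol's plans, but adds that "any major modifications of the primary endpoint definition and/or its analysis will also be reflected in a protocol amendment".

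**The concern.** SAP Appendix 2.1 treats a decline in DAS28 as improvement. With the difference taken as MR minus IR, a positive value therefore means MR did worse. To rule out MR being worse by 0.6 or more, the whole interval must lie below 0.6, so its upper bound must be below 0.6. Requiring only the lower bound to be below 0.6 asks merely that the interval not lie wholly at or above the margin. That shows no more than a failure to prove MR inferior by 0.6.

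This is the trial's single confirmatory decision. Protocol 9.2.4 rests the conclusion on the primary analysis alone, and 9.2.5 excludes non-inferiority testing elsewhere. If the protocol text were applied as written, the type I error would not be controlled, and the same data could pass under one document and fail under the other.

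**Working it through.** **Inputs (Protocol 9.1):** SD 1.3, 100 per arm, margin 0.6, one-sided alpha 0.025, power 90%, assumed true difference 0, stated half-width 0.36.

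**Reproducing the plan's own figures**

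- SE = 1.3 × √(2/100) = 0.1838.
- Half-width = 1.96 × 0.1838 = 0.360, against 0.36 stated.
- n per arm = 2 × 1.3² × (1.960 + 1.282)² / 0.6² = 98.7, rounded up to 99 (198 in total), against 200 stated.
- Power at 100 per arm = Φ(0.6/0.1838 − 1.96) = Φ(1.30) = 90.4% (90.1% by noncentral t), against 90% stated.

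The power and sample size formulae assume a test that succeeds when the upper bound of MR minus IR is below 0.6. The design section is therefore built on the SAP's rule.

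**Point estimate needed to pass**

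- Protocol 9.2.2 (lower bound < 0.6): estimate < 0.6 + 0.360 = 0.960.
- SAP (upper bound < 0.6): estimate < 0.6 − 0.360 = 0.240.

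For example, an estimate of 0.50 has a 95% interval of 0.14 to 0.86. It is non-inferior under 9.2.2 and not under the SAP.

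**Chance of declaring non-inferiority when the true MR minus IR difference is d**

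- Protocol 9.2.2: Φ((0.6 − d)/SE + 1.96)
- Summary, read as MR minus IR: 1 − Φ((−0.6 − d)/SE + 1.96)
- SAP: Φ((0.6 − d)/SE − 1.96)

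| True d | Protocol 9.2.2 | Summary, read as MR − IR | SAP |
|---|---|---|---|
| −0.6 (MR better) | about 100% | 2.5% | about 100% |
| 0 | about 100% | 90.4% | 90.4% |
| +0.3 | 99.98% | 99.8% | 37.1% |
| +0.6 (null boundary) | 97.5% | about 100% | 2.5% |
| +0.8 | 80.8% | about 100% | 0.1% |
| +0.9 | 62.9% | about 100% | 0.02% |

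In 100,000 simulated trials at d = +0.6, the pass rate was 97.50% under 9.2.2 and 2.46% under the SAP.

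The 97.5% at the margin does not depend on the SD or the sample size. The lower limit of a two-sided 95% interval lies below the true value 97.5% of the time, whatever its width.

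**The Summary rule.** If the difference is read as IR minus MR, lower bound above −0.6 is algebraically the same as upper bound of MR minus IR below 0.6, so it agrees with the SAP. If it is read as MR minus IR, the only direction the protocol defines, it tests the wrong side: it passes almost always when MR is worse by the margin and rarely when MR is better by the margin.

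**The case against.** The strongest reply is that this is a one-word slip and the intended test can be recovered. The hypothesis in 9.2.1, the alpha, power and sample size in 9.1, and both SAP statements all fit the upper-bound rule and no other. Protocol section 9 gives the SAP the detailed methodology, so an analysis run to the SAP has a 2.5% error at the margin. Using the upper bound could be seen as implementing 9.2.1 rather than modifying the plan. The SAP's own amendment note describes its correction as following the protocol amendment, so the sponsor evidently believed the documents agreed. The Summary is incompletely specified rather than plainly wrong. Finally, under the planned true difference of zero, 9.2.2 and the SAP disagree only when the estimate falls between 0.24 and 0.96, in about 9.6% of trials (100% − 90.4%).

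Most of this stands as context. The 97.5% is the error rate of 9.2.2 applied literally, not a forecast of what the sponsor will do, and the Summary is better described as lacking a direction.

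It does not remove the defect. Section 9.2.2 states the direction of subtraction itself, so no choice of sign rescues it, and 9.2.3 makes it the operative rule. SAP 4.2 is set in the italics that the SAP introduction reserves for text taken directly from the protocol, yet the protocol's word is lower. The SAP's departure is thus presented as a quotation instead of being declared. The 9.6% is also the least troubling case: at a true difference of +0.6 the two rules disagree in 95% of trials (97.5% − 2.5%).

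**Conclusion.** The concern holds. The rule in Protocol 9.2.2 is wrong for the hypothesis in 9.2.1 and conflicts with 9.1 and with SAP 4.2 and 8.2.1. Applied as written, it declares non-inferiority in 97.5% of trials when MR is worse by exactly 0.6, instead of 2.5%, and it accepts estimates up to 0.96 instead of 0.24.

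The error rates at the margin require only a valid 95% interval. The 0.96 and 0.24 cut-offs and the rates at other differences rest on SD 1.3, 100 evaluable subjects per arm and a normal approximation. Baseline adjustment in the repeated-measures model, or dropout, would change the SE and hence those figures, but not the 97.5% and 2.5%.

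The SAP rule is correct and gives the stated alpha and power. Because the error lies in the threshold for the sole confirmatory test, and section 9 expects major changes to the primary analysis to appear in a protocol amendment, it must be corrected in the protocol.

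**What to change.** Amend two sentences of the protocol:

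1. **Section 9.2.2:** change lower bound to upper bound.
2. **Protocol Summary, Statistical Method:** state that non-inferiority is concluded if the upper limit of the two-sided 95% interval for MR 11 mg QD minus IR 5 mg BID is below 0.6, in place of the lower-bound and −0.6 wording.

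The protocol then agrees with its own 9.2.1 and 9.1 and with SAP 4.2 and 8.2.1, and the italics in SAP 4.2 become accurate on this point. The cost is one short protocol amendment, with no change to data collection, sample size, analysis model or the SAP rule.

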### **9.2.3. Analysis of Primary Efficacy Endpoint**

The primary efficacy variable of DAS28-4(CRP) will be expressed as a change from baseline. The analysis will be conducted using a linear mixed effect model with repeated measures (MMRM), which will include baseline as a covariate, treatment, visit (week 4 and 12), and treatment by visit interaction as fixed effects. Subjects will be a random effect and unstructured covariance will be assumed. The estimate of treatment difference and the associated 2-sided 95% confidence interval (type-I error [alpha] of 0.025 in each tail) at the primary time point of week 12 will be constructed based on the model. The statistical decision rule is described in Section 9.2.2.

The primary efficacy analysis will use the full analysis set (FAS) which will include all subjects who were randomized and received at least one dose of the randomized investigational drug.

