### 8.1. Statistical Methods

#### 8.1.1. Analysis of Longitudinal Continuous Data

*The analysis will be conducted using a linear mixed effect model with repeated measures (MMRM), which will include treatment (tofacitinib MR 11 mg QD and IR 5 mg BID), visit, and treatment by visit interaction as fixed effects. Subjects will be a random effect and unstructured covariance will be assumed for the within-subject errors. If there are convergence problems with this model, sequential structures will be applied until the problems resolved; autoregressive 1 and compound symmetry.*

If there is modeling of actual values, the explanatory variable of visit will include baseline as one of the longitudinal values. When modeling the change from baseline values, the variable of visit will start with the first post-baseline visit, and the actual baseline value will be included as a covariate. At each visit, estimates of mean values, the mean differences between the treatment groups and the associated 2-sided 95% confidence interval (type-I error [alpha] of 0.025 in each tail) will be derived from the model.

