#### 8.1.2. Analysis of Non Longitudinal Continuous Data

The same approach as in Section 8.1.1 will be applied, except that the model will not include visit, treatment-by-visit interaction, or patient as a random effect. In this case, the model is an analysis of covariance (ANCOVA) model.

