#### **8.2.1.1. Sensitivity/Robustness Analyses**

To support the interpretation of the primary analyses, some robustness or sensitivity analyses will be performed for the primary endpoint. However, the conclusions (non-inferiority) for comparison of the primary endpoint between tofacitinib MR 11 mg QD and IR 5 mg BID group is purely based on results of the primary analysis.

One of the robustness analyses is ‘Per Protocol’ analysis, that is, the same primary analysis for the primary endpoint will be conducted using PPAS rather than the FAS.

Other robustness analyses will be performed using the FAS as follows:

- MMRM model described in Section 8.1.1 with compound symmetry instead of unstructured covariance. Missing values will not be imputed.
- MMRM model described in Section 8.1.1 with unstructured covariance. Missing values will be imputed using the method of MI as described in Section 7.
- ANCOVA model described in Section 8.1.2 at Week 12. Missing values will not be imputed.

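### The primary MMRM assumes one baseline slope for Weeks 4 and 12; a baseline-by-visit term costs almost nothing and makes the Week 12 ANCOVA check easier to read

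*Protocol*

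**What the plan says.** Protocol 9.2.3 analyses change from baseline in DAS28-4(CRP) with an MMRM "which will include baseline as a covariate, treatment, visit (week 4 and 12), and treatment by visit interaction as fixed effects". SAP 8.1.1 gives the same mean model: treatment, "visit, and treatment by visit interaction as fixed effects", and, when change from baseline is modelled, "the actual baseline value will be included as a covariate". For the covariance, "unstructured covariance will be assumed for the within-subject errors". The treatment effect and the covariance may therefore differ between visits, but the baseline effect may not. Neither document gives a reason.

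SAP 8.2.1.1 lists the robustness analyses. The per-protocol, compound-symmetry and multiple-imputation analyses all reuse the 8.1.1 mean model. The remaining one is the "ANCOVA model described in Section 8.1.2 at Week 12. Missing values will not be imputed". Under SAP 8.1.2, "the model will not include visit, treatment-by-visit interaction, or patient as a random effect", so this analysis estimates a baseline slope from Week 12 data only. The non-inferiority conclusion "is purely based on results of the primary analysis", so no robustness analysis can alter it.

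**The concern.** With baseline as a main effect only, change is assumed to depend on baseline DAS28 to the same degree at Week 4 and Week 12. If that is not so, the fitted slope is a GLS-weighted average of the two visit slopes, and the Week 12 difference is adjusted by the wrong amount. Part of any chance baseline imbalance then stays in the estimate, and some precision is lost at the one visit that decides the trial.

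There is also a reading problem. The Week 12 ANCOVA differs from the primary MMRM in two ways at once: it has its own Week 12 slope, and it leaves out subjects who have Week 4 but no Week 12 data. If the two results differ, the reader cannot tell which of these is responsible.

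**Working it through.** **The plan's own figures.** Inputs from Protocol 9.1: margin 0.6, SD 1.3, true difference 0, one-sided alpha 0.025, power 90%, 1:1 allocation.
- n per arm = 2 × [1.3 × (1.960 + 1.282) / 0.6]² = 98.7, so 99; the plan uses 100.
- Power at 100 per arm = Φ(0.6 / (1.3 × √(2/100)) − 1.96) = 90.4%.
- 95% half-width = 1.96 × 1.3 × √(2/100) = 0.360, as stated.

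These figures use the unadjusted SD and take no credit for baseline adjustment.

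**Assumed inputs.** The documents give no baseline SD, baseline slope or between-visit correlation. Assumed here: baseline SD s_B = 1.0, SD of change 1.15 at Week 4 (1.3 at Week 12 is the plan's), residual correlation 0.65, complete data.

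**Formulas.** Let b4 and b12 be the true slopes, v4 and v12 the residual variances (change variance minus b² × s_B²), and c the residual covariance.
- Weight on the Week 12 slope: w = (v4 − c) / (v4 + v12 − 2c).
- Common slope: b_c = (1 − w) × b4 + w × b12; gap g = |b_c − b12|.
- Week 12 variance inflation: g² × s_B² / v12.
- Error left by a one-SE baseline imbalance: g × s_B × √(2/100).

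Worked case, slopes -0.2 and -0.4: v4 = 1.3225 − 0.04 = 1.2825; v12 = 1.69 − 0.16 = 1.53; c = 0.65 × √(1.2825 × 1.53) = 0.9105; w = 0.3720 / 0.9915 = 0.375; b_c = -0.275; g = 0.125; inflation = 0.0156 / 1.53 = 1.0%; error = 0.125 × 0.1414 = 0.018.

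| Slopes, Week 4 / Week 12 | Common slope | Gap | Variance inflation | Error at one SE | Half-width, own vs common slope | Power, own vs common slope |
|---|---|---|---|---|---|---|
| -0.3 / -0.3 | -0.300 | 0 | 0 | 0 | 0.351 vs 0.351 | 91.8% vs 91.8% |
| -0.3 / -0.4 | -0.335 | 0.065 | 0.3% | 0.009 | 0.343 vs 0.343 | 92.9% vs 92.9% |
| -0.2 / -0.4 | -0.275 | 0.125 | 1.0% | 0.018 | 0.343 vs 0.345 | 92.9% vs 92.7% |
| -0.2 / -0.6 | -0.390 | 0.210 | 3.3% | 0.030 | 0.320 vs 0.325 | 95.7% vs 95.1% |

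**Wider range.** With Week 4 residual SD 1.0, baseline SD 0.8-1.2 and residual correlation 0.5-0.7, the one-SE error is 0.016-0.025 for slopes -0.3/-0.5, 0.031-0.043 for -0.2/-0.6 and 0.045-0.055 for a deliberately extreme -0.1/-0.7. Variance inflation is 0.8-2.3%, 3.3-7.8% and 7.2-12.7% respectively. At a 1.96-SE imbalance the largest shift is about 0.11. Common-slope power is at least 91% throughout. The reason is that residual variance at Week 12 is 1.69 − b12² × s_B² + g² × s_B², which stays below the planned 1.69 whenever g is smaller than |b12|.

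**Simulation.** 2,000 trials per scenario, 100 per arm, baseline SD 1.0, Week 4 residual SD 1.0, residual correlation 0.6, slopes -0.3/-0.5 and -0.1/-0.7. Week 12 data were complete, or missing depending on Week 4 response, equally or unequally by arm.
- Bias of the common-slope estimate: at most 0.006 with complete data or equal dropout, about 0.015 with unequal dropout.
- Non-inferiority declared at a true difference of 0.6: 2.7-2.9% with the common slope, 2.1-3.0% with visit-specific slopes (Monte Carlo SE about 0.35 points).
- Power at a true difference of 0: 92.6-95.4% with the common slope. The largest loss against visit-specific slopes was 3.0 points (97.2% to 94.2%, extreme slopes).
- The two MMRMs gave different verdicts in 0.3-1.3% of trials (-0.3/-0.5) and 1.2-3.9% (-0.1/-0.7).

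**Comparison with the ANCOVA.** With complete data, the visit-specific MMRM equals the Week 12 ANCOVA exactly (SD of the difference 0.000). The common-slope MMRM differs from it with SD 0.02 (-0.3/-0.5) to 0.05 (-0.1/-0.7). With missing data the SDs are 0.03-0.05 (visit-specific) and 0.04-0.07 (common). Under unequal dropout the mean gap between the ANCOVA and the common-slope MMRM was 0.03-0.06, so the slope component is of similar size to the missing-data signal.

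**The case against.** A single baseline covariate is a valid pre-specified model, and both documents state it consistently. Several stronger readings are tempting, and the documents do not support them.

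- *The common slope fits neither visit, because the Week 12 slope is usually steeper.* The documents contain nothing on either slope. If they are equal, the slope fits both visits. If they differ, the weighted average can still lie close to one of them.
- *The primary result is biased or error control is lost.* Randomisation makes any baseline imbalance a matter of chance, and the model's standard error carries the extra residual variance (0.171 against an empirical 0.173 in the moderate complete-data case). What remains is conditional error, not bias.
- *The trial is underpowered.* The sample size rests on the unadjusted SD of 1.3, so the lost precision was never relied on.
- *The plan's missing-data check is broken.* SAP 8.2.1.1 does not call the ANCOVA a missing-data check. The multiple-imputation MMRM has that role and shares the primary mean model, so it is like for like on slope. The ANCOVA already provides one analysis free of the common-slope assumption.

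All of this stands and limits the point to efficiency and comparability. Two things survive it. The restriction has no stated reason although removing it costs one parameter. And an ANCOVA that departs from the MMRM would still have two explanations. Adding the term removes one of them; it does not make the two analyses agree when Week 12 data are missing.

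**Conclusion.** This is a minor improvement to the primary model, not an error in it. The single slope is a fact of the text; that it misfits Week 12 is only a possibility. For slopes of -0.2 to -0.3 at Week 4 and -0.4 to -0.6 at Week 12, the cost is about 0.3-3.3% of Week 12 variance and up to 0.03 DAS28 points at a one-SE imbalance, against a margin of 0.6 and a half-width of 0.36. It is zero with equal slopes. These sizes rest on the assumed baseline SD, Week 4 SD and correlation; the less favourable values shown raise them to 7.8% and 0.043 for -0.2/-0.6. In no case examined was there material bias or type I error inflation, or power below 90%. The ANCOVA point needs no particular size: if the slopes differ, a gap between it and the MMRM mixes slope with the handling of subjects without Week 12 data.

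**What to change.** Before unblinding, add a baseline-by-visit fixed effect to the primary DAS28-4(CRP) MMRM in Protocol 9.2.3 and SAP 8.1.1, and estimate the Week 12 difference and its interval from that model. Change the matching sentence under Statistical Method in the Protocol Summary. The per-protocol, compound-symmetry and multiple-imputation analyses take their model from SAP 8.1.1 and would follow. Using the term in the other change-from-baseline MMRMs is optional, for consistency.

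The cost is one degree of freedom and the wording. Because the term changes the deciding model, it should be documented in a protocol amendment as well as in the SAP; Protocol Section 9 requires this for major changes to the primary analysis. Introduced after unblinding, it would be a post hoc change. The sample size need not change.
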